4.1.2.3. Influence of Treatment on OSA Severity. Compared with the stretching control (24.4 ± 5.6 to 28.9 ± 6.4), exercise training elicited a significant reduction (32.2 ± 5.6 to 24.6 ± 4.4) in AHI ($F_{1,40} = 9.54$, $P < 0.01$).¹⁹ The magnitude of effect for supine AHI ($g = -0.46$) was similar to that for total AHI ($g = -0.45$), and the amount of time spent supine did not change from pre- to post-intervention. Treatment success, defined as post-intervention apnea-hypopnea index < 20 and reduction $\geq 50\%$ from baseline, was noted in 25% and 7% of the exercise and stretching participants, respectively. Treatment response ($\geq 20\%$ reduction in AHI) was found in 63% and 21% of the exercise and stretching participants, respectively (Fisher exact test, $p=0.02$).

4.1.2.4. Psychometric Variables.²⁰ Compared with the stretching treatment, exercise elicited significant improvements in depressive symptoms, fatigue, and vigor, and several aspects of health-related quality of life ($P < .05$). Scores on the Epworth Sleepiness Scale and the Functional Outcomes of Sleepiness Questionnaire (FOSQ) also improved following exercise versus control to a similar degree in terms of effect sizes ($d > 0.5$), though these changes were not statistically significant with the sample size tested. The proposed sample of N=90 has adequate power for showing statistically significant changes in the FOSQ.

4.1.2.5. Cardiovascular Measures.²¹ For the previous study, we also recruited a control group (n=9) of individuals who had an AHI of < 15 , but were otherwise similar to the experimental group, in terms of age, BMI, etc. Baseline assessments of heart rate recovery from maximal exercise were compared between the experimental subjects (who had AHI of ≥ 15) and the control subjects, who did not undergo the intervention. Heart rate recovery following maximal exercise, a well-established marker of parasympathetic reactivation and SNS withdrawal following exercise, was significantly blunted in the OSA participants compared with the control participants, as assessed at 1 min ($P=.03$), 3 min ($P=.02$), and 5 min post-exercise ($P=.03$). Moreover, impaired heart rate recovery was significantly correlated with OSA severity. Following exercise training, the OSA subjects had a significant improvement in heart rate recovery, indicating improved autonomic regulation. In the proposed study, we will assess the effects of the treatments on blood pressure and heart rate variability.

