5.9. Sample Size and Power. The power calculations are based on our previous study and other published studies. We found an AHI reduction from 32.2 ± 5.6 SD to 24.6 ± 4.4 (7.6 or 24%) following a 12-week exercise protocol, and the attrition rate was 11%.¹⁹ The standard deviation of the change in AHI was large (13), perhaps because of the relatively short intervention duration and small sample size compared with what are proposed. In a recent meta analysis of the effect of dietary weight loss on AHI, we find an average reduction of AHI of 34% in studies involving weight loss of approximately 10% over intervention durations of 12-20 weeks.¹⁸ Based on this finding, we assume a reduction of total AHI from 32.2 ± 5.6 to 21.25 ± 5.2 following the Weight Loss Alone treatment (10.9 or ~34% reduction). A previous study indicated a 46% reduction in total AHI (from 21.7 ± 9.0 to 11.8 ± 6.8) following exercise and weight loss.²⁷ Based on these data, in calculating power, we assume decreases in AHI of increasing magnitude will be observed following exercise alone, weight loss alone, and exercise + weight loss. We assume a reduction of AHI from 32.2 ± 5.6 to 17.3 ± 5.2 (14.9 or 46% reduction) after exercise + weight loss, and we assume 10% attrition. In our power calculations, the overall significance level is set at $\alpha = 0.05$. To insure we will have sufficient testing power, order-restricted tests are not considered in power estimation, but this type of testing will be applied in our data analyses to test the hypothesized pattern.

To ensure power for the **Primary Hypothesis (Compared with exercise alone and weight loss alone, exercise+weight loss will elicit significantly greater improvements in AHI)** we consider weight loss alone vs. exercise+weight loss. We set the significance level at 0.025 to adjust for multiple testing. With $n=30$

per treatment, the power is 86% to detect an average difference of 4 (14.9 vs 10.9, or 46% vs 34%) in AHI reduction between the treatments assuming treatment standard deviations of 5. The power is 82.2% with a 10% attrition. We expect higher statistical power to compare exercise alone vs. exercise+weight loss.

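### The 86%/82.2% power for the primary comparison rests on an unsourced SD of 5 for AHI reduction, which the same section's own figures (13 observed, 12.5 used elsewhere) do not support as an unconditional input

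*Combined protocol and SAP*

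**What the plan says.** All of this is in the combined protocol and SAP.

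- **Section 5.9, primary hypothesis.** The comparison used for power is weight loss alone against exercise + weight loss, at significance level 0.025. The target is a difference of 4 (14.9 against 10.9) "in AHI reduction between the treatments assuming treatment standard deviations of 5". Stated power is 86% with 30 per arm and 82.2% with 10% attrition.
- **Section 5.9, the team's own trial.** "We found an AHI reduction from 32.2 ± 5.6 SD to 24.6 ± 4.4". On the spread of the change itself: "The standard deviation of the change in AHI was large (13"), which the plan attributes tentatively to short duration and small sample.
- **Section 5.9, inputs for the two compared arms.** "we assume a reduction of total AHI from 32.2 ± 5.6 to 21.25 ± 5.2 following the Weight Loss Alone treatment"; and for the combination, "We assume a reduction of AHI from 32.2 ± 5.6 to 17.3 ± 5.2". No pre-post correlation is given.
- **Section 5.9, cited exercise-plus-weight-loss study.** AHI fell from 21.7 ± 9.0 to 11.8 ± 6.8, with the ± not labelled. Section 3.3.3.2 gives its size as N = 9.
- **Section 5.9, Secondary Hypothesis 2.** For exercise alone, the AHI reduction is set at 7.6 ± 12.5.
- **Section 4.1.2.3.** The same trial results appear without an SD label ("exercise training elicited a significant reduction (32.2 ± 5.6 to 24.6 ± 4.4) in AHI"), with an effect size g of -0.45 for total AHI.
- **Section 5.10.** The planned primary analysis is an ANCOVA of post-intervention AHI adjusted for baseline and other covariates.

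**The concern.** The power of a two-arm comparison of change depends directly on the SD of change. Section 5.9 uses 5 for the primary hypothesis and 12.5 for Secondary Hypothesis 2, and reports 13 as observed. It does not say why the primary comparison should have well under half the spread. The reasons it gives for a smaller SD (longer treatment, larger sample) are applied only to the step from 13 to 12.5, and a larger sample does not reduce a population SD.

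This is the only power justification for the primary hypothesis. If the true SD is well above 5, a real 4-point advantage of the combination would more often than not be missed, and a null result would be wrongly read as evidence against it. The 82% upper bound and the figure of about 65% for Secondary Hypothesis 1 rest on the same SD.

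**Working it through.** **1. Reproduce the plan's figure.** Two-sample t-test, noncentral t, difference 4, SD 5, one-sided 0.025; noncentrality = 4 / (5 × √(2/n)).
- n = 30: 86.1%. n = 27: 82.2%. Both match.
- Largest SD that keeps 80% power at n = 27: 5.15.

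**2. Confirm that 12.5 is really used.** Secondary Hypothesis 2, paired one-sided t at 0.017, mean 7.6, SD 12.5: 86.0% (n = 30) and 81.6% (n = 27), against the stated 86.0% and 82%.

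**3. Can 5 be derived from the assumed 5.6 and 5.2?** If these are SDs, change SD = √(5.6² + 5.2² − 2r × 5.6 × 5.2).
- r = 0.50: 5.41, power 80.4%/76.0%.
- r = 0.573: 5.00.
- ANCOVA residual = 5.2 × √(1 − r²), at most 5.2, so power is at least 83.4%/79.2%.

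So 5 is reasonable if, and only if, the ± values are SDs.

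**4. Are they SDs?** In the team's trial, pre and post SDs of 5.6 and 4.4 allow a change SD of at most 5.6 + 4.4 = 10.0. The reported 13 would need r = (5.6² + 4.4² − 13²)/(2 × 5.6 × 4.4) = −2.40, which is impossible. Two supporting checks from section 4.1.2.3:
- Net change = (24.6 − 32.2) − (28.9 − 24.4) = −12.1. With g taken as net change over pooled baseline SD (formula assumed), reading ± as SDs gives −12.1/5.6 = −2.16. Reading ± as standard errors, with 16 to 27 of the 43 in the exercise arm (split assumed), gives a pooled SD of 26.0 to 26.8 and g of −0.45 to −0.47. The reported value is −0.45.
- If F = 9.54 is read as a test on change, its standard error is 12.1/√9.54 = 3.92. The change SD is then 12.8 for an equal split and 12.4 for 27/16, close to 13.

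**5. ANCOVA residual on the standard-error reading.** For exercise-arm n of 16 to 27, the pre SD is 22.4 to 29.1 and the post SD 17.6 to 22.9. With change SD 13, r is about 0.81 to 0.90 and the residual SD = post SD × √(1 − r²) is 9.9 to 10.2, so about 10.

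**6. The exercise-plus-weight-loss study (9.0, 6.8), read as SDs.**
- Change SD 5.0 needs r = (9.0² + 6.8² − 25)/(2 × 9.0 × 6.8) = 0.835.
- At r = 0.57 the change SD is 7.6, power 52.0%/47.7%. The ANCOVA residual is 5.6, power 77.8%/73.3%.
- The ANCOVA residual 6.8 × √(1 − r²) falls to 5 at r of about 0.68.

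**7. Power over the range** (one-sided 0.025, 30/27 per arm). The last column is the detectable difference at 80% power with 27 per arm.

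| SD | Basis | Difference 4 | Secondary Hypothesis 1, 3.2 (80% of 4) | Combination vs exercise alone, 14.9 − 7.6 = 7.3 | Detectable |
|---|---|---|---|---|---|
| 5 | plan | 86.1%/82.2% | 68.4%/63.6% | >99.9%/>99.9% | 3.9 |
| 8 | illustrative | 47.8%/43.8% | 33.1%/30.2% | 93.5%/90.8% | 6.2 |
| 10 | inferred (step 5) | 33.1%/30.2% | 22.9%/21.0% | 79.4%/74.9% | 7.8 |
| 12.5 | used, exercise alone | 22.9%/21.0% | 16.2%/15.0% | 60.4%/55.8% | 9.7 |
| 13 | observed, exercise | 21.5%/19.8% | 15.3%/14.2% | 57.1%/52.6% | 10.1 |

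**The case against.** The strongest defence is that 13 and 12.5 are exercise-only values for unadjusted change, whereas the comparison is between two weight-loss arms and will be analysed by ANCOVA. The study closest to the combination arm (9.0 and 6.8) gives a change SD of 5.0 at r = 0.835, which lies within the correlations inferred in step 5. Over r of 0.82 to 0.90 its change-score power is 83.6% to 95.8% with 30 per arm and 79.5% to 93.7% with 27. So 5 has a possible basis inside the document. That stands, with limits: N = 9, a lower baseline (21.7 against 32.2), an unlabelled ±, and no correlation stated. The plan does not say that 5 came from there.

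Three stronger readings are tempting but not supported.

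- **That true power is 20% to 23%.** This transfers exercise-only change SDs to other arms and ignores baseline adjustment. Secondary Hypothesis 2 does not settle it: the plan says power in the other arms will be greater because effects are larger, but gives no SD for them. The other covariates and the order-restricted tests could add an unquantified amount, although section 5.9 leaves order-restricted tests out of its estimate.
- **That the 5 is proven to come from standard errors.** The bound in step 4 shows an inconsistency in the team's own trial. The ± 5.2 values are new assumptions for other treatments, and the g check needs an assumed formula and arm split.
- **That 0.025 fails as a two-sided Bonferroni level.** The section works one-sided: Secondary Hypothesis 2 says so, and all six Table 3 powers reproduce at one-sided 0.05 with n = 30. The level 0.025 is then 0.05/2 for two directional comparisons. Stating the sidedness would be a clarification only.

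**Conclusion.** The arithmetic is right, but its key input is not supported. The 86%/82.2% holds only if the SD (of change, or the ANCOVA residual) is about 5, and with 27 per arm 80% is lost above 5.15. The document does not derive that value. Its assumed inputs carry forward a ± 5.6 that is probably a standard error, and the alternative basis depends on an unstated correlation from nine participants. Over the SDs that the section states or that can be inferred from it, power for a 4-point difference runs from 86.1%/82.2% down to 21.5%/19.8%.

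The contradiction between 5.6, 4.4 and 13 needs no assumption beyond all three being SDs from the same participants. The value of 10 rests on the standard-error reading and an assumed arm split; 8 is illustrative. The documents do not establish which SD will apply to the two weight-loss arms, so the conclusion is that the stated power must be conditional, not that any one lower figure is the true one.

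**What to change.** 1. Check the ± 5.6, ± 4.4 and ± 5.2 values in sections 4.1.2.3 and 5.9 against their source, and relabel any that are standard errors.
2. Give the source of the SD of 5 and the pre-post correlation or ANCOVA residual that it assumes, or replace it.
3. Restate 86%/82.2% as conditional on the SD. Show power at 5, 8, 10 (marked as inferred), 12.5 and 13, with the 9.0/6.8 study as a further scenario, and the detectable difference at 80% power with 27 per arm (3.9, 6.2, 7.8, 9.7 and 10.1).
4. Make the 82% bound and the 65% for Secondary Hypothesis 1 conditional in the same way, and give power for the exercise-alone comparison over the same range.
5. Drop larger sample size as a reason for a smaller SD.

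As a clarification, add that the 0.025 is one-sided. The cost is some rewording and one short table. The stated power becomes less favourable. Sample size, analysis and conduct do not change.

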For **Secondary Hypothesis 1, Compared with exercise alone and weight loss alone, exercise + weight loss will elicit significantly greater improvements in OSA at 3-month follow-up**, we anticipate decreases in compliance, resulting in greater within-treatment variability and/or lower between-treatment differences, and less powerful between-treatment tests. As such, we consider 82% to be an upper bound power estimate of this hypothesis. If, for example, at follow-up, the magnitude of the effect of condition were only 80% of that anticipated at post-test, power to detect significant differences would be approximately 65%.

For **Secondary Hypothesis 2, Compared with baseline, each treatment will elicit significant improvements in AHI**, the power calculation is based on paired one-sided t-tests to test the reduction of AHI. Since there are 3 treatments, multiple-testing Bonferroni-adjusted significance level is set at $0.05/3=0.017$. For exercise alone, from our preliminary data, we set the mean±SD reduction in AHI (baseline minus post-treatment) at 7.6 ± 12.5 (24% reduction) for the power calculation. The standard deviation is smaller than in our preliminary study because of the longer duration and larger sample size. With $n=30$, tests should have power of 86.0% to detect such a post-exercise difference. With 10% attrition, our tests should have power of 82% to detect this change. Also, we propose a 16 wk treatment, which is a longer than in our previous study and may result in larger reduction with smaller variance. We expect that the AHI reduction will be at least as great as seen in our previous study. Because we expect that weight loss alone and exercise+weight loss will elicit larger effects than exercise alone, the power to detect changes in AHI will be greater for these other treatments.

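### Section 5.9 claims higher power for exercise alone vs exercise+weight loss than the computed 86%/82.2%, but its own SD of 12.5 for exercise alone is not compatible with both statements

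*Combined protocol and SAP*

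**What the plan says.** Section 5.9 words the Primary Hypothesis against both single treatments: "Compared with exercise alone and weight loss alone, exercise+weight loss will elicit significantly greater improvements in AHI". For the test level it says "We set the significance level at 0.025 to adjust for multiple testing", without stating whether the test is one- or two-sided. It then works through one of the two comparisons, weight loss alone vs exercise+weight loss: "the power is 86% to detect an average difference of 4 (14.9 vs 10.9, or 46% vs 34%) in AHI reduction", "assuming treatment standard deviations of 5", and "The power is 82.2% with a 10% attrition".

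The other primary comparison has no figure. It gets one sentence: "We expect higher statistical power to compare exercise alone vs. exercise+weight loss".

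Under Secondary Hypothesis 2, the same section gives the planning values for the exercise-alone arm: "we set the mean±SD reduction in AHI (baseline minus post-treatment) at 7.6 ± 12.5 (24% reduction) for the power calculation". It explains that 12.5 is already lower than the preliminary study's SD (reported earlier in 5.9 as 13) because treatment will be longer and the sample larger.

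Section 5.10 plans a three-group ANCOVA of post-intervention AHI with order-restricted contrasts, and a Bonferroni correction where several non-independent tests are made.

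**The concern.** The sentence about higher power is what lets 86%/82.2% represent the whole Primary Hypothesis. If the uncomputed comparison is nearly certain to succeed, the computed one is the limiting step and its power is close to the power of the whole. That is so if exercise alone also has an SD of 5. The plan's only explicit SD of AHI reduction for that arm is 12.5, two and a half times as large and close to the observed 13. A larger expected difference (7.3 rather than 4) does not automatically make up for that.

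At stake is how the sample size is justified and how a miss is read. A non-significant result against exercise alone could be taken as evidence that adding weight loss does nothing, when the comparison was less well powered than the plan implies.

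**Working it through.** **Inputs, all from 5.9.** Mean AHI reductions: exercise alone 7.6, weight loss alone 10.9, exercise+weight loss 14.9. SD of reduction: 5 (primary calculation), 12.5 (exercise alone, Secondary Hypothesis 2), 13 (observed earlier). n = 30 per arm, or 27 after 10% attrition. Level 0.025.

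**Method.** Power = P(T > t_crit), with T noncentral t and noncentrality δ / √((SD₁² + SD₂²)/n).

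**Step 1: reproduce the printed figures.** Weight loss alone vs exercise+weight loss, δ = 14.9 − 10.9 = 4, SD 5 and 5.
- n=30: SE = √(50/30) = 1.291, noncentrality 3.10, power 86.1%.
- n=27: SE = √(50/27) = 1.361, noncentrality 2.94, power 82.2%.

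Both match at one-sided 0.025. Two-sided 0.025 gives 78.5%/73.5% and does not match, so one-sided 0.025 is used below.

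**Step 2: check that 12.5 is a working value.** A paired one-sided t-test with 7.6/12.5 at level 0.017 gives 86.0% (n=30) and 81.6% (n=27), against the printed 86.0% and 82%. The plan did compute with 12.5.

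**Step 3: the uncomputed comparison.** Exercise alone vs exercise+weight loss, δ = 14.9 − 7.6 = 7.3.
- SD 5 and 5: power above 99.9% at either n.
- SD 12.5 and 5, Welch: SE = √((156.25 + 25)/30) = 2.458, noncentrality 2.97, power 82.5%. At n=27, SE = 2.591, noncentrality 2.82, power 78.2%.
- SD 13 and 5, Welch: 79.9%/75.3%.
- The exercise-alone SD at which the two comparisons have equal power is about 11.8.

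**Step 4: one pooled variance, same SDs (12.5, 5, 5).** The average variance is (156.25 + 25 + 25)/3 = 68.75, so the standard error used in each test is √(2 × 68.75/30) = 2.141 at n=30. It is too small for the exercise-alone comparison (true SE 2.458) and too large for the weight-loss-alone comparison (true SE 1.291). Simulation gives the powers in the table.

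**Step 5: all scenarios, n=30 / n=27, one-sided 0.025.** Joint power is by simulation of 400,000 trials with the shared exercise+weight loss arm.

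| SDs (exercise alone; weight loss alone; exercise+weight loss) | Weight loss alone vs exercise+weight loss | Exercise alone vs exercise+weight loss | Both |
|---|---|---|---|
| 5; 5; 5 | 86%/82% | >99.9%/>99.9% | 86%/82% |
| 12.5; 5; 5, Welch | 86%/82% | 82%/78% | 73%/66% |
| 12.5; 5; 5, one pooled variance | 43%/37% | 89%/86% | 41%/34% |
| 12.5 in all arms | 23%/21% | 60%/56% | 19%/17% |

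Only the first row supports both the printed figures and the sentence, and it needs an exercise-alone SD that the next paragraph of 5.9 does not use. At two-sided 0.025 the second row becomes 73.6%/68.2% for the exercise-alone comparison and 60%/53% for both.

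**The case against.** The strongest reply is that the sentence is wrong about the ordering only in a mixed scenario that the plan never spells out. Nowhere does 5.9 say that exercise alone is more variable than exercise+weight loss. It expects more power in the other two arms because of larger effects, not smaller SDs, and it lists similar before-and-after SDs for all arms. With any common SD, 5 or 12.5, the exercise-alone comparison is the stronger one because its difference is larger. It is also the stronger one with a single residual variance, the usual form of the ANCOVA planned in 5.10, even with SDs of 12.5, 5 and 5. In the Welch scenario the shortfall is only about 4 points, and 12.5 is not far above the break-even of 11.8.

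This stands. A reader might infer that exercise alone vs exercise+weight loss is simply the weaker comparison; the documents do not support that without conditions. It does not rescue the text, though: each reading that keeps 12.5 and the sentence's ordering takes the 86%/82.2% away.

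A reader might also infer that the plan's joint power is 73%/66%. That too goes beyond the documents. The wording of the hypothesis points to both comparisons being required, but splitting alpha suits separate claims, and the plan does not say which applies. In the same Welch scenario, an either-or rule at 0.025 gives 96%/94%, and requiring both at an unsplit one-sided 0.05 gives about 84%/79%. The printed 86%/82.2% is labelled as the power of one named comparison, so it is not in itself a wrong number.

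Finally, baseline adjustment could reduce the SDs, and 5.9 suggests that longer treatment may reduce variance. But no baseline correlation is given, and 12.5 already includes an allowance for duration.

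**Conclusion.** The concern holds as an inconsistency in the power justification. Section 5.9 uses two SDs, 5 and 12.5, that cannot both describe the exercise-alone arm, and its claim about the second primary comparison is safe beside 86%/82.2% only with the smaller one. Once 12.5 is used, either the second comparison is slightly weaker than the computed one (about 82%/78%) or the computed one is far weaker than printed (43%/37% with a pooled variance, 23%/21% with 12.5 throughout). If both comparisons must succeed at one-sided 0.025, power is between about 73%/66% and 19%/17%, depending on the SDs and the variance model.

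These figures rest on the plan's mean reductions, one-sided 0.025 (the level that reproduces the print) and no gain from covariate adjustment. The point should be corrected because the sample size relies on the sentence. It does not show that 30 per arm is the wrong number, and no single joint figure can be called the plan's own until the SDs are settled.

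**What to change.** In 5.9:

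1. Reconcile the SDs of 5 and 12.5 for AHI reduction. State one SD per arm, with its basis, and use it in both the primary and the Secondary Hypothesis 2 calculations.
2. Replace the sentence about higher power with a computed power for exercise alone vs exercise+weight loss at n=30 and n=27. Use the SD the plan sets for exercise alone and a variance model that matches the analysis in 5.10. Recompute weight loss alone vs exercise+weight loss under the same model, and state whether the test is one- or two-sided.
3. State whether the Primary Hypothesis requires both comparisons. If it does, give the joint power with its assumptions, and do not let 86%/82.2% stand for the whole hypothesis.

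Step 1 comes first: printing 73%/66% now would carry forward an SD of 5 that is itself in question.

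Keep 30 per arm. The cost is some rewording and a short recalculation, with no change to participants, visits or data collection. The downside is a less favourable stated power.

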For **Secondary Hypothesis 3, Compared with exercise alone and weight loss alone, exercise + weight loss will elicit significantly greater improvements in measures of co-morbidity**, we use PSQI, systolic blood pressure, and hemoglobin a1c for power calculations. Power is estimated based on two-sample t-tests on the changes (post-treatment minus baseline) of each variable. Having repeated measures for some of these variables will further increase power. Similar treatment effects are assumed for weight loss alone and exercise alone. In this hypothesis, since the outcomes of interests were chosen based on previous studies instead of random selection, alpha for each test is set at 0.05. For Hypothesis 3, $n=30$ per treatment will result in power of ~80% on all the tests except for SBP with minimum detectable differences determined based on our preliminary data (**Table 3**). The power is close to 80% for PSQI and hemoglobin a1c, but 42-47% for systolic blood pressure, assuming 10% attrition. There is clearly sufficient power to detect baseline-to-post improvements for the co-morbidity variables following each individual treatment. Here we focus on effects of weight loss only and exercise only. At alpha of .05, for PSQI, the detectable average reduction is set at 1.5 with standard deviation of 1.8 (for both treatments). Estimated power is 99% with 30 subjects in each group and assuming 10% attrition. For SBP, power is 96% to detect a reduction of 6.7 with standard deviation of 10 with 30 subjects in the group and 10% attrition. Finally, for Ha1c, power is >.99 to detect an average reduction of 0.2% with standard deviation 0.1% assuming 10% attrition. In summary, with 30 subjects in each of the three treatment groups, we are confident that our tests will have power of 80% for most outcome variables.

Table 3. Statistical power under different reduction scenarios for Secondary Hypothesis 3.

PSQI *Reduction=1.5 SD _{diff} =1.8		SBP Reduction=6.7 SD _{diff} =10		Ha1c Reduction=0.2 (%) SD _{diff} =0.1 (%)	
#Diff	Power	Diff	Power	Diff (%)	Power
1.15	78.8%	3.8	42.5%	0.07	85.0%
1.26	85.0%	4.12	47.3%	0.077	90.4%

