5.10. Statistical Analysis. We will first examine univariate and bivariate statistics to determine the distributional characteristics of study variables and to identify potentially relevant background covariates and confounders. For the **Primary Hypothesis and Secondary Hypotheses 1 and 3**, we will use an analysis of covariance (ANCOVA) approach to examine treatment effects on post-intervention (i.e., immediate post-test for Primary Hypothesis and Secondary Hypothesis 3; 3-month follow-up for Secondary Hypothesis 1) outcome values (i.e., AHI scores for Primary Hypothesis and Secondary Hypothesis 1; comorbidity measures for Secondary Hypothesis 3), with treatment as the primary independent variable, and adjusting for baseline outcome value, intervention dose (percentage of sessions attended), baseline outcome value, age, sex,

duration of OSA diagnosis, plus any other relevant covariates. We will test for ordering of treatment means (not adjusted for covariates) via order-restricted tests within the R package flexisoreg. Next, we will test for overall differences among treatment groups on post-treatment AHI values with order-restricted comparisons (isotonic contrasts) of covariate-adjusted means to test for the predicted ordered patterning of the three treatment means. For **Secondary Hypothesis 2**, we will examine the effect of time point (pre- vs. post-treatment) on AHI scores at each treatment level (i.e., test “simple main effects” of time) in the context of a repeated measures ANCOVA. Analyses will be based on an intent-to-treat plan. For each hypothesis, overall alpha will be set at .05, with a Bonferroni correction applied when multiple non-independent tests are conducted. **Missing data** due to dropout or other causes will be addressed with analyses of multiply-imputed datasets generated with SAS PROC MI based on models drawing on all available participant data.

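### Table 3 gives the power of one comparison, but Secondary Hypothesis 3 is worded against both single treatments; power that both comparisons succeed is lower and is not reported

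*Combined protocol and SAP*

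**What the plan says.** Section 5.9 words Secondary Hypothesis 3 as "Compared with exercise alone and weight loss alone, exercise + weight loss will elicit significantly greater improvements in measures of co-morbidity". Its power basis is given as "Power is estimated based on two-sample t-tests on the changes (post-treatment minus baseline) of each variable", with "alpha for each test is set at 0.05". No sidedness is stated for this hypothesis. The section adds: "Similar treatment effects are assumed for weight loss alone and exercise alone".

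Table 3 lists two assumed differences per outcome with their power. The table's title shows that the two rows are effect scenarios, not the two comparisons. The text summarises the table by saying that 30 participants "per treatment will result in power of ~80% on all the tests except for SBP". It describes power after 10% attrition as close to 80% for PSQI and HbA1c and 42–47% for SBP, and closes: "we are confident that our tests will have power of 80% for most outcome variables".

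Section 5.10 sets a different-looking rule for each hypothesis: "overall alpha will be set at .05, with a Bonferroni correction applied when multiple non-independent tests are conducted".

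**The concern.** The hypothesis names two comparisons: the combined arm against exercise alone, and the combined arm against weight loss alone. Table 3 reports the power of one.

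For the Primary Hypothesis this matters little, because section 5.9 powers the harder comparison (against weight loss alone) and expects the other to be easier. For Secondary Hypothesis 3 the single treatments are assumed to be similar, so the two comparisons are equally hard. The chance of winning both is then clearly below the chance of winning one.

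A reader who takes the 80% statements as the chance of showing that the combined arm beats both single treatments would be misled. A null result on PSQI or HbA1c would be read against more power than the trial had for that claim.

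**Working it through.** **Inputs (section 5.9 and Table 3).** There are 30 per arm, "with 30 subjects in each of the three treatment groups", and 27 per arm after 10% attrition (30 × 0.9). SDs of change are 1.8 (PSQI), 10 (SBP) and 0.1 (HbA1c, %). Differences are 1.15 and 1.26; 3.8 and 4.12; 0.07 and 0.077. The same difference applies to both comparisons, because the single treatments are assumed similar.

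**Step 1: reproduce Table 3.** The power of one two-sample t-test comes from the noncentral t distribution with 2n − 2 degrees of freedom and noncentrality δ = d / (SD × √(2/n)). For PSQI 1.15 at n = 30, δ = 1.15 / (1.8 × √(2/30)) = 2.474. The one-sided 0.05 critical value is 1.672 and the power is 78.8%, as printed. All six entries reproduce this way to within 0.1 point. Two-sided 0.05 gives 68.2/76.0% (PSQI), 30.4/34.8% (SBP) and 76.0/83.5% (HbA1c), which do not match. Neither does 27 per arm. Table 3 is therefore one comparison, one-sided 0.05, before attrition.

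**Step 2: both comparisons.** The two differences share the combined arm. Their covariance is SD²/n and each variance is 2·SD²/n, so their correlation is 0.5. Joint power is approximately Φ₂(δ − z, δ − z; 0.5). For PSQI 1.15 at n = 27, δ = 1.15 / (1.8 × √(2/27)) = 2.347 and δ − 1.645 = 0.702, giving 63.2%. Simulating three arms (1,000,000 trials, both t-tests significant) gives 61.9%. The simulated values are used below; simulation error is about 0.1 point.

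| Outcome, difference | One, n=30 (= Table 3) | Both, n=30 | One, n=27 | Both, n=27 | Both, n=27, one-sided 0.025 |
|---|---|---|---|---|---|
| PSQI 1.15 | 78.8% | 67.1% | 74.9% | 61.9% | 48% |
| PSQI 1.26 | 85.0% | 75.7% | 81.4% | 70.6% | 57% |
| SBP 3.8 | 42.5% | 26.1% | 39.5% | 23.5% | 14% |
| SBP 4.12 | 47.3% | 30.7% | 44.0% | 27.6% | 17% |
| HbA1c 0.07 | 85.0% | 75.7% | 81.4% | 70.6% | 57% |
| HbA1c 0.077 | 90.4% | 83.8% | 87.4% | 79.3% | 68% |

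All columns but the last use one-sided 0.05. The last column is the level for two-sided 0.05, and also for the section 5.10 Bonferroni correction applied to two one-sided comparisons (0.05/2).

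**Step 3: separate the two causes.** For PSQI 1.15, attrition alone takes 78.8% to 74.9% (3.9 points). The second comparison takes 74.9% to 61.9% (13.0 points).

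**Step 4: the attrition statement.** With 27 per arm and one comparison, PSQI is 74.9–81.4% and HbA1c 81.4–87.4%, so close to 80% is fair for a single test. SBP is 39.5–44.0%. The stated 42–47% is the 30-per-arm value from Table 3.

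**The case against.** **The plan speaks per test.** Alpha, the power statement and the closing sentence all refer to individual tests, and Table 3 is correct on that basis. This stands: a reader might infer that Table 3 contains an arithmetic error, and it does not.

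**No rule requires both comparisons to succeed.** A reader might infer from the hypothesis wording that the plan demands both. The documents do not say so, and the alpha handling is compatible with separate claims. The Primary Hypothesis has the same structure and is powered at 0.025 to adjust for multiple testing; section 5.10 applies Bonferroni. Splitting alpha is needed when either comparison may be claimed alone, not when both must be won. This also stands. What remains is that the hypothesis as worded is about both, and no figure is given for that claim.

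**The planned analysis may be more powerful.** Section 5.10 adjusts for baseline, and section 5.9 notes that repeated measures would help. With equal pre and post variances and a pre–post correlation r, ANCOVA multiplies the change-score variance by (1 + r)/2. If r were 0.5 (an assumption), joint power at n = 27 would be about 75% for PSQI 1.15, and 83% and 90% for the two HbA1c scenarios. At r = 0.85, PSQI would be 66% and 74%. Section 5.6.3 quotes a PSQI test–retest reliability of 0.85, but that is not a correlation across 16 weeks of treatment. The documents therefore give no basis for choosing within this range, and Table 3 takes no credit for it.

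**It is a secondary hypothesis, and low SBP power is already disclosed.** That limits the importance of the point but does not remove it.

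**Conclusion.** The point holds as one of incomplete reporting. The figures of about 80% are per-comparison power. For the claim that the combined arm beats both single treatments, power on the plan's change-score t-test basis at one-sided 0.05 is 67–84% (PSQI and HbA1c) and 26–31% (SBP) at 30 per arm. At 27 per arm it is 62–79% and 24–28%, and at one-sided 0.025 it falls to 48–68% and 14–17%.

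These figures rest on equal effects of the single treatments (the plan's assumption), the Table 3 differences and SDs, normal changes and no gain from covariates.

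Two further readings go too far. It is not true that no scenario reaches 80%: HbA1c 0.077 gives 84% at 30 per arm, though none reaches 80% at 27 per arm on this basis. Nor is the whole shortfall due to the second comparison, since attrition accounts for part of it. The SBP attrition figure is a separate small inconsistency that holds whichever success rule is meant.

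**What to change.** In section 5.9:

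1. Label Table 3 as power per comparison with 30 per arm.
2. State the sidedness for Secondary Hypothesis 3, and reconcile the 0.05 per test with the Bonferroni rule in section 5.10. Do this first, because the remaining figures depend on it.
3. On that alpha, add the power that both comparisons succeed, at 30 and at 27 per arm.
4. Replace 42–47% for SBP after attrition with 39.5–44.0% if one-sided 0.05 is kept, or with the value for the alpha chosen.
5. Qualify the two 80% sentences as per comparison, and give the joint power beside any statement that the combined arm beats both single treatments.

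The sponsor should also say whether the two comparisons are to be claimed separately or only together; this review does not assume either. The changes need no extra patients and no change of design. The cost is that the stated figures become less favourable.
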